10.9.9 SF-36v2 Acute Version Short Form 36-Health Survey Questionnaire v2

SF-36v2® Health Survey Single-Item Acute Recall for Handheld Device

Item Name	Question Text	Answer Text 1	Answer Text 2	Answer Text 3	Answer Text 4	Answer Text 5	Answer Text 6
	Your Health and Well-Being						
	This survey asks for your views about your health. This information will help keep track of how you feel and how well you are able to do your usual activities. Thank you for completing this survey!						
	For each of the following questions, please select the one response that best describes your answer.						
SF36v2_GH1	In general, would you say your health is:	Excellent	Very good	Good	Fair	Poor	
SF36v2_HT	Compared to one week ago, how would you rate your health in general now?	Much better now than one week ago	Somewhat better now than one week ago	About the same as one week ago	Somewhat worse now than one week ago	Much worse now than one week ago	
	The following questions are about activities you might do during a typical day. Does your health now limit you in these activities? If so, how much?						
SF36v2_PF01	Does your health now limit you in vigorous activities , such as running, lifting heavy objects, participating in strenuous sports? If so, how much?	Yes, limited a lot	Yes, limited a little	No, not limited at all			
SF36v2_PF02	Does your health now limit you in moderate activities, such as moving a table, pushing a vacuum cleaner, bowling, or playing golf? If so, how much?	Yes, limited a lot	Yes, limited a little	No, not limited at all			
SF36v2_PF03	Does your health now limit you in lifting or carrying groceries? If so, how much?	Yes, limited a lot	Yes, limited a little	No, not limited at all			
SF36v2_PF04	Does your health now limit you in climbing several flights of stairs? If so, how much?	Yes, limited a lot	Yes, limited a little	No, not limited at all			
SF36v2_PF05	Does your health now limit you in climbing one flight of stairs? If so, how much?	Yes, limited a lot	Yes, limited a little	No, not limited at all			
SF36v2_PF06	Does your health now limit you in bending, kneeling, or stooping? If so, how much?	Yes, limited a lot	Yes, limited a little	No, not limited at all			
SF36v2_PF07	Does your health now limit you in walking more than a mile ? If so, how much?	Yes, limited a lot	Yes, limited a little	No, not limited at all			
SF36v2_PF08	Does your health now limit you in walking several hundred yards ? If so, how much?	Yes, limited a lot	Yes, limited a little	No, not limited at all			
SF36v2_PF09	Does your health now limit you in walking one hundred yards ? If so, how much?	Yes, limited a lot	Yes, limited a little	No, not limited at all			
SF36v2_PF10	Does your health now limit you in bathing or dressing yourself? If so, how much?	Yes, limited a lot	Yes, limited a little	No, not limited at all			
	During the past week , how much of the time have you had any of the following problems with your work or other regular daily activities as a result of your physical health?						

Item Name	Question Text	Answer Text 1	Answer Text 2	Answer Text 3	Answer Text 4	Answer Text 5	Answer Text 6
SF36v2_RP1	During the past week , how much of the time have you cut down on the amount of time you spent on work or other activities as a result of your physical health?	All of the time	Most of the time	Some of the time	A little of the time	None of the time	
SF36v2_RP2	During the past week , how much of the time have you accomplished less than you would like as a result of your physical health?	All of the time	Most of the time	Some of the time	A little of the time	None of the time	
SF36v2_RP3	During the past week , how much of the time were you limited in the kind of work or other activities as a result of your physical health?	All of the time	Most of the time	Some of the time	A little of the time	None of the time	
SF36v2_RP4	During the past week , how much of the time have you had difficulty performing the work or other activities as a result of your physical health (for example, it took extra effort)?	All of the time	Most of the time	Some of the time	A little of the time	None of the time	
	During the past week , how much of the time have you had any of the following problems with your work or other regular daily activities as a result of any emotional problems (such as feeling depressed or anxious)?						
SF36v2_RE1	During the past week , how much of the time have you cut down on the amount of time you spent on work or other activities as a result of any emotional problems (such as feeling depressed or anxious)?	All of the time	Most of the time	Some of the time	A little of the time	None of the time	
SF36v2_RE2	During the past week , how much of the time have you accomplished less than you would like as a result of any emotional problems (such as feeling depressed or anxious)?	All of the time	Most of the time	Some of the time	A little of the time	None of the time	
SF36v2_RE3	During the past week , how much of the time have you done work or other activities less carefully than usual as a result of any emotional problems (such as feeling depressed or anxious)?	All of the time	Most of the time	Some of the time	A little of the time	None of the time	
SF36v2_SF1	During the past week , to what extent has your physical health or emotional problems interfered with your normal social activities with family, friends, neighbors, or groups?	Not at all	Slightly	Moderately	Quite a bit	Extremely	
SF36v2_BP1	How much bodily pain have you had during the past week?	None	Very mild	Mild	Moderate	Severe	Very severe
SF36v2_BP2	During the past week , how much did pain interfere with your normal work (including both work outside the home and housework)?	Not at all	A little bit	Moderately	Quite a bit	Extremely	
	These questions are about how you feel and how things have been with you during the past week. For each question, please give the one answer that comes closest to the way you have been feeling.						

 $SF-36v2^{\textcircled{@}}\ Health\ Survey\ \textcircled{@}\ 1992,\ 2000,\ 2010,\ 2012\ Medical\ Outcomes\ Trust\ and\ QualityMetric\ Incorporated.\ All\ rights\ reserved.\\ SF-36v2^{\textcircled{@}}\ Health\ Survey\ Acute,\ United\ States\ (English))$

Item Name	Question Text	Answer Text 1	Answer Text 2	Answer Text 3	Answer Text 4	Answer Text 5	Answer Text 6
SF36v2_VT1	How much of the time during the past week did you feel full of life?	All of the time	Most of the time	Some of the time	A little of the time	None of the time	
SF36v2_MH1	How much of the time during the past week have you been very nervous?	All of the time	Most of the time	Some of the time	A little of the time	None of the time	
SF36v2_MH2	How much of the time during the past week have you felt so down in the dumps that nothing could cheer you up?	All of the time	Most of the time	Some of the time	A little of the time	None of the time	
SF36v2_MH3	How much of the time during the past week have you felt calm and peaceful?	All of the time	Most of the time	Some of the time	A little of the time	None of the time	
SF36v2_VT2	How much of the time during the past week did you have a lot of energy?	All of the time	Most of the time	Some of the time	A little of the time	None of the time	
SF36v2_MH4	How much of the time during the past week have you felt downhearted and depressed?	All of the time	Most of the time	Some of the time	A little of the time	None of the time	
SF36v2_VT3	How much of the time during the past week did you feel worn out?	All of the time	Most of the time	Some of the time	A little of the time	None of the time	
SF36v2_MH5	How much of the time during the past week have you been happy?	All of the time	Most of the time	Some of the time	A little of the time	None of the time	
SF36v2_VT4	How much of the time during the past week did you feel tired?	All of the time	Most of the time	Some of the time	A little of the time	None of the time	
SF36v2_SF2	During the past week , how much of the time has your physical health or emotional problems interfered with your social activities (like visiting with friends, relatives, etc.)?	All of the time	Most of the time	Some of the time	A little of the time	None of the time	
	How TRUE or FALSE is each of the following statements for you?						
SF36v2_GH2	I seem to get sick a little easier than other people.	Definitely true	Mostly true	Don't know	Mostly false	Definitely false	
SF36v2_GH3	I am as healthy as anybody I know.	Definitely true	Mostly true	Don't know	Mostly false	Definitely false	
SF36v2_GH4	I expect my health to get worse.	Definitely true	Mostly true	Don't know	Mostly false	Definitely false	
SF36v2_GH5	My health is excellent.	Definitely true	Mostly true	Don't know	Mostly false	Definitely false	
	SF-36v2® Health Survey © 1992, 2000, 2010, 2012 Medical Outcomes Trust and QualityMetric Incorporated. All rights reserved. SF-36® is a registered trademark of Medical Outcomes Trust. (SF-36v2® Health Survey Acute, United States (English))						

Amendment Protocol Version No. 02 (Clean)

10.9.10 Home Administration Study Drug Diary (example)

CQGE031G12303B – Home Administration Study Drug Diary

	Questions/answers	Triggers
Q1	If you /participant are a female who can get pregnant, please perform a pregnancy test prior to injecting the study treatment. If the result is positive DO NOT inject the study treatment and inform the site personnel.	Only show to female participants
Instruction screen	Study treatment pre-filled syringe injections Reminder: The dose includes 2 injections. At each site visit, please return unused/used kit packaging.	
Q2	Has the study drug been injected? Yes / No	If Yes, go to Q3. If No, skip Q3, go to Q4 and end of the diary.
Q3	How many injections did you have? 1 / 2	If 1, go to Q5, Q6, Q7, and Q9. If 2, skip Q4 and go to Q5, Q6, Q7, Q8, and Q9.
Q4	You had 0 or 1 injection, select the reason: Participant decision Parent/Caregiver decision Adverse Event Technical Problems Pregnancy	
Q5	Please enter the date of injection(s): Date picker	
Q6	Please enter the time of injections: Time picker (Hour: minutes)	
Q7	Select the site of the 1 st injection. Left Thigh Right Thigh Left Abdomen Right Abdomen Left Upper Arm Right Upper Arm	
Q8	Select the site of the 2 nd injection. Left Thigh Right Thigh Left Abdomen Right Abdomen Left Upper Arm Right Upper Arm	
Q9	Who performed the injections? Myself Parent/Caregiver Study site personnel	

CRF Case Report/Record Form (paper or electronic)

CRO Contract research organization

CSR Clinical study report
CV Coefficient of variation

DBL Database Lock

DBPCFC Double Blind Placebo Controlled Food Challenge

DLS Dose limiting symptom
EAIR Exposure adjusted
ECG Electrocardiogram

eCRF Electronic case report form
eCRS Electronic case retrieval strategy

EOS End of study

FAIM Food Allergy Independent Measure
FAQLQ Food Allergy Quality of Life Questionnaire

FAS Full Analysis Set

FcεRI IgE (high affinity) receptor

h Hour HR Heart rate

HRQoL Health-Related Quality of Life

IgE Immunoglobulin E (specific and un-specific for the study allergen)

IgG Immunoglobulin G
IS Independent Statistician

L Liter

CCI

MedDRA Medical dictionary for regulatory activities

mg Milligram(s)
mL Milliliter(s)
mm Millimeter

mmHg Blood pressure unit millimeters of mercury

MR Maximum responder

ms Millisecond

OFC Oral Food Challenge PD Pharmacodynamic(s)

CC

PRO	Patient Reported Outcomes
PT	Preferred term
q4W	Every 4 weeks
RR	Responder rate
SAE	Serious Adverse Event
SAF	Safety analysis set
SAP	Statistical analysis plan
SC	Subcutaneous
SCq4W	Subcutaneous injection every 4 weeks
SD	Standard deviation
CCI	
SMQ	Standardized MedDRA Query
SOC	System organ class
SPT	Skin Prick Test
TEAE	Treatment-emergent adverse events
TESAE	Treatment-emergent serious adverse events
Total IgE	Drug-bound and free IgE
μL	Microliter

1 Introduction

The purpose of this Statistical Analysis Plan (SAP) is to describe the statistical analyses mentioned in version of the Phase 3 study CQGE031G12303B protocol. This document covers the statistical and analytical plans for the Clinical Study Report (CSR).

After thorough consideration, Novartis decided to terminate the study early. This was a consequence of a broader Novartis company strategic decision and was by no means due to the detection of any potential safety signal. Due to the early termination, the scope of analysis will be limited.

1.1 Study design

This is a multi-center, double-blind, 3-year, extension study to evaluate the long-term safety and efficacy of ligelizumab in participants who completed ligelizumab Phase III studies in food allergy. This is a basket extension study which enables the participants from planned multiple Phase III "core" studies to roll over to this extension study (CQGE031G12303B) once the participants have completed a "core" study and agreed to consent to participate in Study CQGE031G12303B. Please refer below to the schematic diagram of the study, including transition from core study (Figure 1-1).

Participants will receive up to 3 years treatment with ligelizumab after which they will enter a follow-up period for 16 weeks. During the study, participants will undergo allergy testing by a Skin Prick Test and Oral Food challenge to test the level of desensitization. Accordingly, this study will generate data that should provide guidance relative to the long-term (chronic) use of ligelizumab in food allergic patients in terms of safety, efficacy, pharmaco-dynamics, biomarkers and Quality of Life, and potential discontinuation from treatment.

During the study, treatment will be administered every 4 weeks and, while this can take place in the hospital clinic, some participants will be trained to administer study treatment at home by either the participant or parent/caregiver. Participants at home will record administration of the study treatment on a dosing log and return this to the clinic for review.

[figure not shown]

Figure 1-1 Study design including transition from the core study

DBPCFC: Double Blind Placebo Controlled OFC, OL-OFC: Open Label Oral Food Challenge, MR: Maximum Responder, EOT: End of Treatment, EOFu: End of Follow-Up.

The participants from study CQGE031G12301 will transition into the extension study after completion of the follow-up period (washout) in the core study (Refer Figure 4-1 from the protocol). The end of follow-up visit of the core study will become the first visit of this extension study (Screening/Day 1) for these participants. Some of the assessments at EOFu of the core study will form the baseline at Screening/Day 1 in the extension study. The informed consent must be obtained before initiating any study related activities of the extension study at Screening/Day 1.

1.2 Study objectives, endpoints and estimands

Due to the early termination of the study, purely descriptive analyses will be performed for primary, secondary endpoints, and part of exploratory endpoints.

Table 1-1 Objectives and related endpoints

*	
Objective(s)	Endpoint(s)
Primary objective(s)	Endpoint(s) for primary objective(s)
To evaluate the long-term safety and tolerability of ligelizumab in participants with food allergy	Overall incidence and exposure-adjusted occurrence rates of treatment-emergent AEs and SAEs
Secondary objective(s)	Endpoint(s) for secondary objective(s)
To describe the long-term efficacy of ligelizumab as measured by the tolerance of an allergen food protein during an open-label OFC at scheduled timepoints	 Proportion of participants tolerating a single dose of ≥ 600 mg of peanut protein without dose-limiting symptoms during an open label OFC at scheduled timepoints
 To assess the safety and tolerability of ligelizumab in all participants who administered study treatment at home by self-administration or parent/caregiver 	 Overall incidence and exposure-adjusted occurrence rates of treatment emergent-AEs and SAEs
 To assess the long-term impact of ligelizumab on the health-related quality of life (HRQoL) of patients with food allergy 	 Summaries of total scores in the FAQLQ, FAIM, and SF-36v2 by age and responder (participants and/or parent/caregiver) at scheduled timepoints
Exploratory objective(s)	Endpoint(s) for exploratory objective(s)

1.2.1 Primary estimand(s)

Not Applicable.

1.2.2 Secondary estimand(s)

Not Applicable.

2 Statistical methods

2.1 CCI

2.1.1 General definitions

2.1.1.1

[figure not shown]

2.1.1.3 CCI

2.1.1.4 **CC**

[figure not shown]

2.1.1.5 **CC**

2.1.1.6 **CC**

2.4 Treatments (study treatment, rescue medication, concomitant therapies, compliance)

Study treatment and compliance will be summarized for SAF-1.

2.4.1 Study treatment / compliance

The duration of exposure in weeks to each treatment group will be summarized using descriptive statistics.

Duration of exposure to study treatment will be calculated as the number of weeks between the first dose date and the last dose date exposed to that treatment over the specified period (Duration of exposure = (date of last known study treatment - date of first known study treatment + 28)/7).

In addition, the number of doses, total cumulative dose and number of missed doses will be summarized using descriptive statistics (see Section 2.1.1).

Listings on dose administration records will be provided.

2.4.2 Prior, concomitant and post therapies

Not required for CSR analysis.

2.5 Analysis supporting primary objective(s)

2.5.1 Primary safety endpoint(s)

The primary objective of the study is to assess the long-term safety and tolerability of ligelizumab in participants with food allergy for an additional three-year period after a core study.

Page 15 of 28 Study No. CQGE031G12303B

Primary endpoints are overall incidence and exposure-adjusted occurrence rates (EAOR) of treatment-emergent adverse events (TEAEs) and serious adverse events (TESAEs), however, due to early termination of the study, EAOR will not be calculated.

TEAEs are defined as events that either:

- 1) Where an AE either started after the first dose of extension study treatment and within 16 weeks after the last administered study treatment dose or
- 2) began prior to the first dose of study treatment but increased in severity (based on preferred term) within 16 weeks after the last study treatment.

All participants enrolled into the extension study, regardless of which preceding studies they came from, will be included in the safety analysis. All listings and tables will be presented by treatment dose. All data will be included in the analysis, regardless of rescue medication use.

This analysis will be based on SAF-1.

For all adverse events tables the events that the investigator classified as reactions associated to the Oral Food Challenge (OFC)or Skin Prick Test (SPT) will not be included in reporting of treatment-emergent adverse events (TEAEs).

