9.3.2 Statistical model, hypothesis, and method of analysis

There is no pre-specified hypothesis for the primary endpoints, and no inferential analysis will be done for the primary endpoints.

Summary statistics will be provided.

Summaries will include: 1) the number and percentages of participants with at least one event (incidence rates); and 2) exposure-adjusted occurrence rates (the number of events per participant year of exposure). The following treatment-emergent AE summaries will be provided for the Safety Set 1 (SAF-1), presented by dose and cumulative duration of exposure:

- Overall, by primary system organ class and preferred term,
- Overall, by primary Standardized MedDRA Query (SMQ) and preferred term,
- Overall, by primary system organ class, preferred term and maximum severity,
- Suspected drug-related AEs by primary system organ class and preferred term,
- SAEs by primary system organ class and preferred term,
- AEs leading to permanent discontinuation of study-drug by primary system organ class and preferred term,
- Adverse events of special interest (AESI).

Other tables will be generated to summarize safety data for participants in SAF-1 who restarted study treatment after a protocol mandated interruption period (> 16weeks). Details will be provided in the SAP.

Summaries will be performed as well for non-TEAEs for participants who did not receive any study treatment doses during the extension study (SAF-2).

Separate summaries will be provided for study treatment-related adverse events, death, serious adverse events, and other significant adverse events leading to discontinuation. If a participant reported more than one AE with the same preferred term, the AE with the greatest severity will be presented. If a participant reported more than one AE within the same primary system organ class, the participant will be counted only once with the greatest severity at the system organ class level, where applicable.

Other safety analyses (laboratory data, vital signs, ECG) are described in Section 9.4.2.

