2.5.2.1 Exposure-Adjusted Incidence rate and 95% confidence interval

The EAIR is defined as the number of participants with a specific event divided by the total exposure-time among the participants in the study group. That is, the EAIR is calculated as:

 $EAIR = n / \Sigma t_i$, where n is the number of participants having the i^{th} type event, and t_i is a participant's exposure time and defined as the shortest of the following:

- 1. Time to the first episode of the i^{th} type event (if the event occurs),
- 2. Time to the end of observation period, or
- 3. duration of study treatment plus the 16-week washout period (approximately corresponding to five half-lives) after last treatment dose

The total exposure time of all participants in a treatment group is Σ t_i . The EAIR is interpreted as the number of events occurring in a population per unit time. The exact Poisson 95% confidence interval for the EAIR will be provided as well, where an exact $100*(1-\alpha)\%$ confidence interval will be derived as follows (Garwood 1936, Sahai and Khurshid 1993):

- Lower confidence limit $L = \frac{0.5C_{\alpha/2,2n}}{\sum t_i}$ for n>0, 0 otherwise,
- Upper confidence limit $U = \frac{0.5C_{1-\alpha/2,2n+2}}{\sum t_i}$,

where $C_{\alpha,k}$ is the α th quantile of the Chi-square distribution with k degrees of freedom.

Whenever applicable, exposure adjusted incidence rates will be provided for the type as below:

- 1. TEAE and TESAE: Primary SOC level, PT level
- 2. Further safety analyses are defined in safety analyses (Section 2.8)

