2.5.2.2 Adverse Events (AEs)

The following treatment-emergent AE summaries will be provided by overall and by treatment group for the Safety Set 1 (SAF-1), presented by dose and cumulative duration of exposure:

- Overview of all TEAEs: Number of participants with at least one (Any AE, Any SAE, Any AE related to study drug, Any AE leading to discontinuation of study treatment, Deaths etc.)
- TEAEs by primary system organ class and preferred term,
- TEAEs by primary Standardized MedDRA Query (SMQ) and preferred term,
- TEAEs by primary system organ class, preferred term and maximum severity,
- TESAEs by primary system organ class and preferred term,
- TEAEs leading to permanent discontinuation of study-drug by primary system organ class and preferred term,
- Treatment Emergent Adverse events of special interest (AESI),
- Study treatment-related adverse events by primary system organ class and preferred term,
- Deaths by primary system organ class and preferred term including listing of deaths,

If a participant reported more than one AE with the same preferred term, the AE with the greatest severity will be presented. If a participant reported more than one AE within the same primary system organ class, the participant will be counted only once with the greatest severity at the system organ class level, where applicable.

Separate summaries will be provided for study treatment-related adverse events, death, serious adverse events, and other significant adverse events leading to discontinuation.

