2.7 Exploratory analyses

2.8 Safety analyses

All safety endpoints i.e. AEs, laboratory data and vital signs will be conducted on SAF-1, only wherever required summary and listings will be provided on SAF-2. All listings and tables will be presented by treatment group.

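### On the visible text, exposure and the TEAE window run straight across mandated dosing gaps, and events before a delayed first dose have no clearly specified summary

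*SAP*

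**What the plan says.** **Exposure.** SAP 2.4.1 computes ("date of last known study treatment - date of first known study treatment + 28")/7, for the treatment the participant was "exposed to that treatment over the specified period". The visible text does not define that period.

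**TEAE window.** SAP 2.5.1 counts an event "Where an AE either started after the first dose of extension study treatment and within 16 weeks after the last administered study treatment dose". A second limb admits events that began before the first dose and then worsened. Protocol 9.3.1 has essentially the same definition.

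**EAIR time.** SAP 2.5.2.1 takes the shortest of time to first event, time to end of observation, and "duration of study treatment plus the 16-week washout period".

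**Interruptions.** Under Protocol 4.1.2.1, a participant treated through year one who is MR at Week 52 stops treatment and is re-challenged at Week 68. Treatment restarts then if MR status is lost; otherwise the participant stays off drug up to Week 104. A participant from Study CQGE031G12301 who is still MR on Day 1 receives no extension drug until Week 52, unless an ad hoc challenge leads to an earlier start.

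**Off-drug events.** Protocol 9.3.2 says: "Summaries will be performed as well for non-TEAEs for participants who did not receive any study treatment doses during the extension study (SAF-2"). SAP 2.8 narrows this: "only wherever required summary and listings will be provided on SAF-2". The AE table list in SAP 2.5.2.2 concerns treatment-emergent events on SAF-1.

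**Restart tables.** Protocol 9.3.2 also promises tables for "participants in SAF-1 who restarted study treatment after a protocol mandated interruption period" of more than 16 weeks and leaves the detail to the SAP.

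**The concern.** The design takes some participants off drug for up to a year or more and then puts some of them back on. A rule that looks only at the first and last dose dates treats the whole interval as treated.

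Two consequences follow. First, reported exposure includes time when no drug was given. SAP 2.5.2.2 also presents AE tables by cumulative exposure, so if that uses the 2.4.1 formula the same error carries into those tables. Second, whether an off-drug event is tabulated turns on a later dosing decision and not on when the event happened.

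The delayed first dose is a different mechanism. Here the window opens late, and the one summary meant for untreated participants excludes anyone who is eventually dosed.

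Both matter because the study is meant to inform possible discontinuation of treatment, and that question needs on-drug and off-drug experience to be kept apart.

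**Working it through.** The plan gives no figure on this point. Its one worked precision example (Protocol 9.9.2: 1% of 200, 0.12% to 3.6%) reproduces as 0.121% to 3.565% from 2/200 and is not in dispute.

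**Inputs.** First dose Week 0 (Day 1), dosing every 4 weeks, Week 52 dose given before the challenge, last dose Week 156, end of study Week 172 (Protocol Table 1-4 and 6.2.3). Restart at Week 68 or Week 104 (Protocol 4.1.2.1). Tails of 28 days (SAP 2.4.1) and 16 weeks (SAP 2.5.1). Let L be the week of the last dose and r the week of restart after a Week 52 stop.

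**Step 1: exposure.** SAP formula: L + 4. By episode: (52 + 4) + (L − r + 4). Difference: r − 56.

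**Step 2: TEAE window, and EAIR time for a participant without an event, read as elapsed time.** SAP: L + 16. By episode: (52 + 16) + (L + 16 − r). Difference: r − 68.

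| Restart (L = 156) | Exposure, SAP | By episode | Excess | Window, SAP | By episode | Excess |
|---|---|---|---|---|---|---|
| Week 68 | 160 | 148 | 12 | 172 | 172 | 0 |
| Week 104 | 160 | 112 | 48 | 172 | 136 | 36 |

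The exposure ratios are 160/148 = 1.08 and 160/112 = 1.43; the window ratio at Week 104 is 172/136 = 1.26. Counting in days, with restart one day after the challenge, gives 159.9 against 147.7 and 111.7 weeks for exposure, and 171.9 against 171.7 and 135.7 for the window. The excess depends on r and not on L. Early termination therefore limits how many participants reach a restart, not the error for one who does.

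**Step 3: classification.** Take a Week 52 stopper with a new event at Week 80, which is after Week 52 + 16 = Week 68. If dosing resumes at Week 104, the event lies inside the window and is a TEAE. If dosing never resumes, the window closed at Week 68 and it is not. The participant has been dosed, so SAF-2 as Protocol 9.3.2 describes it does not apply either. With no restart and follow-up to week T, the uncovered time is max(0, T − 68): 0 weeks at T = 68, 36 at T = 104, 104 at T = 172.

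**Step 4: delayed first dose.** A Day-1 MR first dosed on Day 169 (after an ad hoc challenge around Week 24), Day 365 (Week 52) or Day 729 (Week 104) has (169 − 1)/7 = 24, (365 − 1)/7 = 52 or (729 − 1)/7 = 104 weeks on study beforehand. A new event in that time fails the first limb, meets the second only if it worsens, and is outside SAF-2 because the participant was later dosed. The exposure formula is not distorted here, since it starts at the first dose.

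**Step 5: EAIR reading.** SAP 2.5.2.1 does not define treatment duration. Read as elapsed time, Step 2 applies. With the 2.4.1 formula, a Week 52 stopper who never restarts gets 56 + 16 = 72 weeks against a 68-week TEAE window. Read as summed dosed time, the gap would leave the denominator while gap events could still enter the numerator. The term needs a definition on any reading.

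**The case against.** **Unseen text.** SAP 2.1.1 is redacted, 2.2 and 2.2.1 are not shown, and Section 4 shows only its heading. A gap rule, the SAF definitions or a record of dropped tables could sit there, and the undefined period in 2.4.1 may do the same work. This stands, and it makes the remedy conditional. It also disposes of one stronger reading. A reader might infer from the list in SAP 2.5.2.2 that the restart tables of Protocol 9.3.2 have been lost. The documents do not support that, because the tables may be specified or formally dropped in text that cannot be seen.

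**Convention and balance.** The single window follows Protocol 9.3.1, and when EAIR time is elapsed time, events and time in the gap both enter the rate. A reader might infer that the EAIRs are materially biased. That does not follow: the direction depends on the off-drug event rate, a Week 68 restart leaves EAIR time essentially unchanged, and no restart counts are given. The objection does not rescue the exposure summary, which has no offsetting term.

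**Early termination.** The SAP limits its scope, and its 380-day rule for remapping end visits suggests that some participants finished near one year. For them the gap problem is largely empty. The delayed-first-dose problem remains, since it can arise within year one.

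**Other outputs.** Dose counts, cumulative dose, missed doses and dosing listings make gaps traceable, though they do not change how events are counted. Deaths and adjudicated events are listed. SAP 2.5.2.2 also promises separate summaries of related events, deaths and SAEs without repeating that they are treatment-emergent; placed under the treatment-emergent list, their scope is ambiguous. Nor would post-restart anaphylaxis be hidden: it falls inside the TEAE window, the hypersensitivity table and the adjudicated listing.

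**Endpoint.** Events before any extension dose are rightly not TEAEs, so leaving them out does not corrupt the primary endpoint. What is missing is a place to report them.

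**Conclusion.** The concern holds in limited form and is worth correcting. On the visible text, the SAP 2.4.1 formula counts mandated off-drug time as exposure: 12 weeks too many for a Week 52 stop with a Week 68 restart, 48 weeks for a Week 104 restart. The SAP 2.5.1 window makes an event more than 16 weeks after the last pre-gap dose a TEAE only if dosing later resumes. EAIR time is affected in the same way only under the elapsed-time reading; the pooled effect is probably small, of unknown direction, and limited by early termination.

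Separately, new events before a Day-1 MR's delayed first dose that do not worsen have no clearly specified summary. The exceptions are the death and adjudicated-event listings and possibly the separate SAE, death and related-event summaries.

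These conclusions assume that no rule in the unseen SAP sections says otherwise, and that SAF-2 is the never-dosed set described in Protocol 9.3.2. How many participants are affected cannot be derived from the documents.

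**What to change.** First check SAP 2.1.1, 2.2, 2.2.1, Section 4 and the period referred to in 2.4.1. Unless they already provide it:

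1. Derive exposure, TEAE status and EAIR person-time by treatment episode. Each episode runs from its first dose to 28 days after its last dose for exposure, and to 16 weeks after it for TEAE and EAIR, without counting overlapping time twice. Record the change from Protocol 9.3.1 in SAP Section 4.
2. Add to SAP 2.5.2.2 one summary of non-TEAEs in off-treatment time for all enrolled participants, including time before a delayed first dose, with its own person-time.

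As a query only: confirm whether the restart tables of Protocol 9.3.2 are kept or are recorded as dropped in Section 4. The answer is worth having because Protocol 2.3 reports that two of four adjudicated anaphylaxis cases followed a restart and that the reintroduction risk is not yet characterised in this population.

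The cost is a few derivations and one table, from dosing and AE dates already collected.
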